6.6 Definition of Maximum Permissible Dose and Method of Dose Escalation

Dose Limiting Toxicity (DLT): DLT is defined as toxicity or events of Grade 3 or higher (80 points or higher against pain) in two or more events at the surgery site among swelling, tenderness, range of motion, and pain in any one visit. DLT is also defined as adverse drug reaction of Grade 3 or higher in the Common Toxicity Criteria Adverse Events (CTCAE), Version 4.0, with the exception of the following events and that they are unresolved for 7 consecutive days, despite medical interventions:

- ✓ Abnormal results in lab test (Acidosis, Hyponatremia, Hyperbilirubinemia, etc.)
- ✓ Fatigue, defined as not relieved by rest; limiting self-care ADL
- ✓ Pain, defined as severe pain; limiting self-care ADL
- ✓ Headache, defined as severe pain in various parts of the head, limiting self-care ADL Fever, defined as > 40.0 degrees C (> 104.0 degrees F) for > 24 hours

Maximum Tolerated Dose (MTD): If DLT occurs in 2 or fewer patients at the Dosage B level, the MTD will be Dosage B. If DLT occurs in 3 or more patients treated with Dosage B then the MTD will be Dosage A. If DLT occurs in 3 patients treated with Dosage A then the MTD will not have been determined in this study design.

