Approximate Duration of Patient Participation	Each patient will undergo a 6-week screening period for eligibility and a 12- month follow-up observation period for both the primary (safety) and secondary (efficacy) evaluations following administration of CARTISTEM [®] . Also each patient will undergo a 24-month follow-up visit for a long term patient assessment.

page 6 of 137

CONFIDENTIAL: These all contents herein are the sole property of MEDIPOST Co., Ltd. Any reproduction or distribution of this document without the written consent of MEDIPOST Co., Ltd is prohibited. Copyright © 2017 MEDIPOST Co., Ltd.

Approximate Duration of Study	The estimated duration of the study for the primary evaluation is approximately 12 months, with an additional 12 month extension for the long-term patient assessment phase.
Safety Evaluation	General General safety will be evaluated via the following assessments: AEs, routine clinical laboratory tests (hematology, clinical chemistry, and urinalysis), thrombin generation (PT and aPTT), immunogenicity tests (T cell subset), vital signs, physical exams, ECGs, and MRI for tumorigenicity.
	 Adverse Events To assess the safety of CARTISTEM[®], the course and degree of swelling, tenderness, range of motion and pain will be determined. DLT is defined as toxicity or adverse event of Grade 3 or higher [80 points or higher for pain] in two or more events at the surgery site among swelling, tenderness, range of motion, and pain, in any one visit. DLT is also defined as adverse drug reaction of Grade 3 or higher in the Common Toxicity Criteria Adverse Events (CTCAE), Version 4.0, with the exception of the following events and that they are unresolved for 7 consecutive days, despite medical interventions: Abnormal results in lab test (Acidosis, Hyponatremia, Hyperbilirubinemia, etc.) Fatigue, defined as not relieved by rest; limiting self-care ADL Pain, defined as severe pain in various parts of the head, limiting self-care ADL Fever, defined as >40.0 degrees C (> 104.0 degrees F) for > 24 hours

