6.5 Dose Escalation

This clinical trial will employ the following dose escalation scheme:

[figure not shown]
A total of 12-18 patients will be enrolled and treated with CARTISTEM[®] for dose limiting toxicity (DLT) evaluation. Initially, 6 patients with lesion sizes of $2 - 5 \text{ cm}^2$ will be assigned to Dosage A and treated with $0.5 - 1.25 \times 10^7$ MSCs; if dose limiting toxicity is not observed at the 3 month time point for the first clinical efficacy evaluation, then another 6 patients with lesion sizes of above 5 cm² will be assigned to Dosage B and treated with more than 1.25 x 10^7 MSCs for further safety evaluation. If a DLT occurs to one or two patients of the group treated with the dosage A, 3 more patients will be assigned to dosage A. If DLT happens to 3 of the patients who were treated with the dosage A or above, this study will be halted and the FDA and IRB will be notified. The Independent Data Monitoring Committee will perform a comprehensive review of safety (see Section 9.1).

CARTISTEM®

page 24 of 137

CONFIDENTIAL: These all contents herein are the sole property of MEDIPOST Co., Ltd. Any reproduction or distribution of this document without the written consent of MEDIPOST Co., Ltd is prohibited. Copyright © 2017 MEDIPOST Co., Ltd.

If no DLT occurs to any of the dosage A patients, another 6 patients with larger defect sizes will be enrolled and assigned to dosage B. In case of no DLT observed, a total of 12 patients will be enrolled for safety and efficacy evaluation. However, 18 patients could be enrolled if DLT occurs to two patients. If DLT occur 3 or more patients treated with Dosage B, this study will be halted and the FDA and IRB will be notified. The Independent Data Monitoring Committee will perform a comprehensive review of safety (see Section 9.1).

CARTISTEM®

page 25 of 137

CONFIDENTIAL: These all contents herein are the sole property of MEDIPOST Co., Ltd. Any reproduction or distribution of this document without the written consent of MEDIPOST Co., Ltd is prohibited. Copyright © 2017 MEDIPOST Co., Ltd.

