6.7 Expected Adverse Effects and Usage Considerations

6.7.1 Expected Adverse Effects

There has not been any expected adverse effect that is directly related to the administration of CARTISTEM[®], however, mild increase in temperature, pain, nausea, and headache may occur in a response to the administration of allogenic mesenchymal stem cells. In general, adverse effects that may be observed following arthrotomy accompanied by the use of anesthesia include the followings:

- Implant site pain, pruritus, and warmth
- Nausea

CARTISTEM®

page 26 of 137

CONFIDENTIAL: These all contents herein are the sole property of MEDIPOST Co., Ltd. Any reproduction or distribution of this document without the written consent of MEDIPOST Co., Ltd is prohibited. Copyright © 2017 MEDIPOST Co., Ltd.

- Constipation
- Dyspepsia
- Headache
- Dysuria
- Dizziness
- 6.7.2 Usage Considerations
- 1) Sterility should be strictly maintained as the product involves injection into human knee joint cavity.
- 2) Should any serious adverse events occur during the administration period or within 14 days after final injection, the principal investigator must, regardless of whether or not the adverse reaction is thought to be related to the study drug, report the incident to the clinical trial review committee and MEDIPOST Co., Ltd. personnel within 24 hours of occurrence.
- 3) This drug should not be administered intravenously.
- 4) Before mixing the constituting substances of the drug, tap the vial with the fingers to make sure that the cells and the preserving solution mix properly. Do not vortex.
- 5) In order to prevent the intrusion of any foreign materials into the syringe, wipe the needle point and insertion area of the vial with ethanol before inserting the needle into the vial.

7 Investigational Product

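### The second DLT criterion in 6.6 is mis-worded: on either plausible reading, a listed Grade 3+ reaction that persists for 7 days is not a DLT

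*Combined protocol and SAP*

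**What the plan says.** Section 6.6 gives two routes to a DLT. The first is local: Grade 3 or higher (80 points or more for pain) "in two or more events at the surgery site among swelling, tenderness, range of motion, and pain in any one visit". The second is any adverse drug reaction of CTCAE v4.0 Grade 3 or higher, "with the exception of the following events and that they are unresolved for 7 consecutive days, despite medical interventions". Five items follow: abnormal laboratory results (open-ended), fatigue, pain, headache, and fever above 40.0 °C for more than 24 hours.

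The same clause stands in the synopsis under Study Overview and again under Safety Evaluation ("with the exception of the following events and that they are unresolved for 7 consecutive days").

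The DLT count then drives these decisions:
- Dosage A, no DLT: "If no DLT occurs to any of the dosage A patients, another 6 patients with larger defect sizes will be enrolled".
- Dosage A, one or two: "If a DLT occurs to one or two patients of the group treated with the dosage A, 3 more patients will be assigned".
- Dosage A, three: "If DLT happens to 3 of the patients who were treated with the dosage A or above, this study will be halted".
- Dosage B: with two or fewer, the MTD is Dosage B. Otherwise "If DLT occurs in 3 or more patients treated with Dosage B then the MTD will be Dosage A", and 6.5 halts the study.

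**The concern.** A grace period for manageable toxicities normally says that certain events are not DLTs unless they persist. Here the persistence condition is joined to the exception itself. Read that way, the exempt events are those that are both listed and unresolved at 7 days. A severe headache that defeats a week of treatment is left out, and one that clears in three days is counted.

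Safety is the primary objective and each cohort starts with 6 patients, so the definition has to work case by case and in the same way at both centers. Three of the listed items overlap with what 6.7.1 anticipates from the cells: "mild increase in temperature, pain, nausea, and headache may occur in a response to the administration of allogenic mesenchymal stem cells". That section does not suggest Grade 3 events, so the overlap shows relevance, not frequency.

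**Working it through.** The plan states no figure to reproduce. The check is on the logic of the clause, and then on the decisions that use it.

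**1. Readings.** The clause is ungrammatical, so three rules are compared.
- *Natural reading*: *they* means the listed events. Exempt = listed and unresolved at 7 days.
- *Second parse*: listed events never count, and *they* means the remaining Grade 3+ reactions, which count only if unresolved at 7 days.
- *Apparent intent*: listed events count only if unresolved at 7 days, and unlisted events always count. This is inferred. The reference to failed medical treatment makes sense only if persistence is what turns a manageable event into a DLT.

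**2. Is a related Grade 3+ reaction a DLT under the second criterion?**

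| Reaction | Natural | Second parse | Apparent intent |
|---|---|---|---|
| Listed, clears in 3 days | Yes | No | No |
| Listed, unresolved at 10 days | **No** | **No** | **Yes** |
| Unlisted, clears in 3 days | Yes | No | Yes |
| Unlisted, unresolved at 10 days | Yes | Yes | Yes |

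With 5 listed types and 2 durations there are 10 listed cases. The natural reading disagrees with the intent in 10 of 10, the second parse in 5 of 10 (the persistent ones). For unlisted events the disagreements are 0 of 2 and 1 of 2. The row that fails on both readings is the persistent listed reaction.

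**3. Does the first criterion catch it?** It needs two local signs at one visit. It cannot be met by fever, fatigue, headache or a laboratory abnormality, nor by knee pain alone. Related Grade 3 knee pain lasting 10 days without a second Grade 3 sign is therefore not a DLT by either route.

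**4. Is it corrected elsewhere?** Sections 6.5 and 9.1 do not restate the definition. The charter in Appendix 5 says stopping rules will be set before the first data review, but it does not define a DLT.

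**5. Effect of one reclassified patient on the decisions.**
- Dosage A: 0 to 1 changes opening Dosage B into adding 3 patients; 1 to 2 changes nothing; 2 to 3 changes adding 3 patients into a halt.
- Dosage B: 0 to 1 and 1 to 2 leave the MTD at B; 2 to 3 moves it to A and halts the study.

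**6. Illustration on assumed rates (none are in the documents).** Let q be the chance per patient of a listed related Grade 3+ event, and f the share of these unresolved at 7 days, with no other DLTs. For 6 patients, P(at least one DLT) = 1 − (1 − p)^6, where p = q(1 − f) on the natural reading, 0 on the second parse and qf as intended.

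With q = 0.20 and f = 0.25:
- natural: p = 0.15, 1 − 0.85^6 = 0.623
- second parse: 0
- intended: p = 0.05, 1 − 0.95^6 = 0.265

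| f (q = 0.20) | Natural | Second parse | Intended |
|---|---|---|---|
| 0.10 | 0.696 | 0 | 0.114 |
| 0.25 | 0.623 | 0 | 0.265 |
| 0.50 | 0.469 | 0 | 0.469 |
| 0.75 | 0.265 | 0 | 0.623 |

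Over q from 0.10 to 0.50 and f from 0.10 to 0.75, the natural reading gives 0.141 to 0.972 and the intended rule 0.059 to 0.940. The error can go in either direction. At f = 0.50 the probabilities agree, but different patients are counted.

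**The case against.** The strongest reply is that the sentence is garbled rather than reversed, and that nobody would apply it backwards. Appendix 5 requires a board meeting before Dosage B starts and a review of individual subject data, and 6.5 adds a full safety review if the study is halted. Clinicians who see the evident purpose would count the 10-day reaction. The prior experience in the administration dosage section (no treatment-related serious events in 7 + 50 = 57 Korean patients at the same cell density) suggests that few such cases would arise.

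Part of this stands. A reader might infer that every listed event is certain to be misclassified in both directions. The documents do not support that, because the 10-of-10 count belongs to the natural reading alone. A reader might also infer that unsafe escalation is likely. No event rate is given, so that does not follow either. A serious event is not the same as a Grade 3 event, so the Korean figure lowers the likelihood without settling it. The rule also counts patients, so a further event in a patient who already has a DLT changes nothing.

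The ambiguity does not remove the defect, since both readings drop the persistent listed reaction. Relying on each center to repair the sentence silently is also not a definition.

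A second objection is aimed at the repair, and it is right. If the list is kept unchanged, a related fever above 40 °C lasting 20 hours (Grade 3 in Appendix 4, but not the listed item) would be an immediate DLT, while one lasting 5 days would be exempt. The lists also differ as they read in the available text. Study Overview repeats two items and shows no fatigue or headache; Safety Evaluation has no separate headache item and attaches the head description to pain. This may be an artefact of PDF conversion, but the repair should not depend on it.

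**Conclusion.** Wrong as written. The second DLT criterion does not capture a listed, related Grade 3+ reaction that persists for 7 days, on either plausible reading. On the more natural one it also counts listed reactions that resolve. One affected patient is enough to change the action at two of the three steps in the Dosage A count (0 to 1, 2 to 3) and at one of three for the MTD at Dosage B (2 to 3).

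This rests on two things: the intent is inferred from the clause and not stated anywhere, and the patient has no DLT by another route. The probabilities above rest on assumed rates and show only that the effect can be large and of either sign. They do not forecast this trial. Unlisted Grade 3+ reactions are unaffected on the natural reading, and the two-sign criterion is unaffected throughout.

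**What to change.** In 6.6 and in both synopsis places, replace the second criterion with:

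*Any adverse drug reaction of CTCAE v4.0 Grade 3 or higher is a DLT whatever its duration, except that the events listed below are a DLT only if they remain unresolved for 7 consecutive days despite medical intervention.*

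Use the 6.6 list in all three places. Reword the fever item, for example as *Fever > 40.0 degrees C* with no minimum duration, so that a shorter fever is not treated more strictly than a longer one. Leave the two-sign criterion as it is.

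The cost is one sentence, a harmonised list and one reworded item, in three places. Sample size, visit schedule, tests and escalation thresholds stay the same. The sponsor should confirm the intent with the clinical team when making the change. One consequence to confirm is that a laboratory abnormality above Grade 3 that resolves within 7 days would then not be a DLT, because the laboratory item is open-ended.

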CARTISTEM® PHASE I/IIa CLINICAL TRIAL PROTOCOL MP-0201-01

Version 3.2 Date: 15 March, 2017

CARTISTEM® PHASE I/IIa CLINICAL TRIAL PROTOCOL

CARTISTEM®

page 1 of 137

CONFIDENTIAL: These all contents herein are the sole property of MEDIPOST Co., Ltd. Any reproduction or distribution of this document without the written consent of MEDIPOST Co., Ltd is prohibited. Copyright © 2017 MEDIPOST Co., Ltd.

Name of Company Name of Product: Umbilical Cord Blo Ex vivo, Combined	Protocol #: MP-0201-01								
Protocol Title	Evaluation of Safety and Exploratory Efficacy of CARTISTEM [®] , a Cell Therapy Product for Articular Cartilage Defects: A Phase I/IIa Clinical Trial in Patients with Focal, Full-thickness Grade 3-4 Articular Cartilage Defects of the Knee								
Clinical Phase	Phase I/IIa								
Study Overview	dy Overview CARTISTEM [®] will be administered at doses ranging from 0.5×10 ⁷ to 2.25×10 ⁷ hUCB-MSC (0.25×10 ⁷ cells/cm ² ; 0.5 mL/cm ² with 0.5×10 ⁷ MSC/mL) to patients with focal, full-thickness, Grade 3-4 articular cartilage defects of ≥ 2cm ² in size. Safety: Patient safety will be assessed step-wise with increasing levels of total hUCB-MSC and HA exposure: a total of 12 patients will be enrolled and treated with CARTISTEM [®] to evaluate whether dose limiting toxicity (DLT) is detected. DLT is defined as toxicity or adverse event of Grade 3 or higher [80 points or higher for pain] in two or more events at the surgery site among swelling, tenderness, range of motion, and pain in any one visit. DLT is also defined as adverse drug reaction of Grade 3 or higher in the Common Toxicity Criteria Adverse Events (CTCAE), Version 4.0, with the exception of the following events and that they are unresolved for 7 consecutive days, despite medical interventions: ✓ Abnormal results in lab test (Acidosis, Hyponatremia, Hyperbilirubinemia, etc.) ✓ Abnormal results in lab test (Acidosis, Hyponatremia, Hyperbilirubinemia, etc.) ✓ Pain, defined as severe pain; limiting self-care ADL ✓ Pain, defined as severe pain; limiting self-care ADL								
	✓ Fever, defined as > 40.0 degrees C (> 104.0 d	degrees F) for > 24 hours							
	Initially, 6 patients with lesion sizes of 2-5 cm ² w (Dosage A); if dose limiting toxicity is not detect after administration, an additional 6 patients, with	ed during a 12 week period							

page 2 of 137

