Definition: A disorder characterized by a sen sation of marked discontrol in the face. ADL ADL Patigue Fatigue relieved by rest Fatigue not relieved by yest; limiting instrumental ADL Fatigue not relieved by yest, limiting self care ADL - <	Definition: A disord er characte	rized by swelling due to excessive fu	uid a coumulation in the trunk area			
Fatigue Fatigue relieved by rest Fatigue not relieved by rest; limiting instrumental ADL Fatigue not relieved by rest, limiting instrumental ADL Fatigue not relieved by rest, limiting self care ADL -	Facial pain	Mild pain		1742.0 D.V. D.V.C.	8	ŀ
Imiting instrumental ADL Imiting self care ADL Imiting self care ADL Imiting self care ADL Definition: A disorder characterized by a state of generalized weak-ess with a pronounced inability to summon sufficient energy to accomplish daily a ctivities. >40.0 degrees C (>104.0 degrees F) for <=24 hrs	Definition: A disord er characte	rized by a sensation of marked disco	omfort in the face.	n n 1	·	7
Fever 38.0 - 39.0 degrees C (100.4 - 102.2 degrees F) >39.0 - 40.0 degrees C (102.3 - 104.0 degrees C (>104.0 degrees C (>104.0 degrees F) for <=24 hrs			limiting instrumental ADL	limiting selfcare ADL		ŀ
102.2 degrees F) 104.0 degrees F) degrees F) for <=24 hrs	A REAL PROPERTY AND A REAL		The second se		Contraction of the Contract of Contract	in and the second
Flu like symptoms Mild fu-like symptoms present. Moderate symptoms; limiting instrumental ADL. Severe symptoms; limiting self care ADL - - Definition: A disorder characterized by a group of symptoms similar to those observed in patients with the flu. It includes fever, chills, body aches, malaise, loss of appetite an sough . Moderate change in gait (e.g., wide-based, limping or hobbling) Moderate change in gait (e.g., wide-based, limping or hobbling) Moderate change in gait (e.g., wide-based, limping or hobbling) Disabling; limiting selfcare ADL - - Definition: A disorder characterized by walking difficulties. Moderate change in gait (e.g., wide-based, limping or hobbling); assistive device indicated; limiting instrumental ADL. Disabling; limiting selfcare ADL - - Definition: A disorder characterized by walking difficulties. - - - - - Hypothermia -		102.2 degrees F)	104.0 degrees F)	degrees F) for <= 24 hrs	입법 가서 중 맛가? 가장 감상을 하지? 그 것이 없어야 했다 지	Death

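### The DLT exception list exempts drug-related fever above 40.0 C lasting more than 24 hours, which lies above Grade 3, so some isolated severe fever stays out of the DLT count

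*Combined protocol and SAP*

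**What the plan says.** Section 6.6 has two routes to a DLT. The first covers only swelling, tenderness, range of motion and pain at the surgery site. The second counts any adverse drug reaction of CTCAE v4.0 Grade 3 or higher, "with the exception of the following events and that they are unresolved for 7 consecutive days, despite medical interventions". The list that follows holds laboratory results, fatigue, pain, headache and "Fever, defined as > 40.0 degrees C (> 104.0 degrees F) for > 24 hours". The fever item also stands in the Synopsis, under Study Overview ("Fever, defined as > 40.0 degrees C", with the same duration) and under Safety Evaluation ("Fever, defined as >40.0 degrees C (> 104.0 degrees F) for > 24 hours").

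Appendix 4 (CTCAE v4.0, General disorders) gives Grade 3 fever as ">40.0 degrees C (>104.0 degrees F) for <=24 hrs".

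The DLT count drives the rules in Section 6.5. At Dosage A: "If a DLT occurs to one or two patients of the group treated with the dosage A, 3 more patients will be assigned"; with no DLT, Dosage B opens. For halting: "If DLT happens to 3 of the patients who were treated with the dosage A or above, this study will be halted" and "If DLT occur 3 or more patients treated with Dosage B, this study will be halted". Section 6.6 sets the MTD at Dosage B with 2 or fewer DLTs there, and at Dosage A with 3 or more.

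**The concern.** An exception list in a DLT definition normally sets aside the milder or more transient end of the countable range. The fatigue, pain and headache items do this: they use Grade 3 wording (limiting self-care). The fever item sets aside a longer fever than the Grade 3 one, and Grade 3 fever itself is not listed. A patient with a short fever above 40.0 C can therefore count while a patient with a longer one does not.

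Safety is the primary objective, the groups have 6 to 9 patients, and the thresholds are 1 and 3 patients. One misclassified patient can change whether Dosage A is expanded, whether the study halts, and which dose is called the MTD.

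**Working it through.** The plan gives no error rate or operating characteristic for its DLT rule, so there is no stated figure to reproduce. The check is one of definitions, followed by the effect on the decision rules.

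**1. Grade of the excepted fever.** The fever row of Appendix 4 is scrambled in the copy reviewed. One garbled rendering shows more than 24 hours. The legible text and the column order (Grade 1 to 39.0 C, Grade 2 to 40.0 C, then above 40.0 C for up to 24 hours) support 24 hours or less for Grade 3. The Grade 4 cell is not cleanly legible. It follows that a fever above 40.0 C for more than 24 hours lies above Grade 3, and nothing more is claimed.

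**2. Readings of the 7-day clause.** Each reading is applied to a drug-related fever above 40.0 C lasting 20 hours (Grade 3), 5 days or 8 days (both above Grade 3).

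| Reading | 20 h | 5 days | 8 days |
|---|---|---|---|
| Listed events count only if unresolved for 7 days (natural) | DLT | not | DLT |
| Exempt only if listed and unresolved for 7 days (literal) | DLT | DLT | not |
| Listed events never count; others count at once | DLT | not | not |
| Listed events never count; others only after 7 days | not | not | not |
| Every Grade 3+ reaction needs 7 days | not | not | DLT |
| Fever entry is the only countable fever, after 7 days | not | not | DLT |
| Carve-in: fever counts once above 40.0 C for >24 h | not | DLT | DLT |

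On the first six rows at least one fever above Grade 3 is uncounted. Only the carve-in row avoids this. It treats the list as inclusions, although the text introduces it as exceptions, and it drops the 7-day condition.

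**3. What still counts by another term.** Unlisted Grade 3 or higher terms in Appendix 4 count in their own right if drug-related: joint infection needing arthroscopy or arthrotomy, wound infection needing IV antibiotics, sepsis, allergic reaction, cytokine release syndrome. The remaining gap is an isolated drug-related fever with none of these.

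**4. Effect of one uncounted patient on the rules in 6.5 and 6.6.**

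| True count → counted | Dosage A | Dosage B |
|---|---|---|
| 1 → 0 | first 6: three more at A → B opens | no change |
| 2 → 1 | first 6: three more either way | no change |
| 3 → 2 | halt → no halt | halt → no halt; MTD A → B |

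Section 6.5 does not state the action after 1 DLT in 9 at Dosage A.

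**5. How often.** Section 6 reports no treatment-related SAE in 7 + 50 = 57 earlier patients. The one-sided 95% upper limit is 1 − 0.05^(1/57) = 5.1% per patient. It bears on this point only if such a fever would have been an SAE. If the isolated fever has probability p per patient, the chance of at least one in the first 6 is 1 − (1 − p)^6:

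- p = 1% (assumed): 1 − 0.99^6 = 5.9%
- p = 5% (assumed): 1 − 0.95^6 = 26.5%

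If 1/6 is counted as 0/6, the three added patients are skipped. With an overall DLT rate q, the chance that they would have produced the two further DLTs needed for a halt is 3q²(1 − q) + q³:

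- q = 5.1%: 0.8%
- q = 10%: 2.8%
- q = 1/6: 7.4%

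The values of q are assumptions.

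The estimated rate hardly moves: the exact (Clopper–Pearson) 95% interval is 0–46% for 0/6 and 0.3–48% for 1/9.

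**The case against.** The strongest reply is that few patients could be affected. Sustained fever after joint surgery with allogeneic cells would often come with an infection or immune reaction that counts under its own term. A reader might infer that severe fever in general escapes the DLT count. Appendix 4 does not support that, and the point is limited to isolated fever.

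Other controls also exist. SAEs go to the sponsor and IRB within 24 hours (Section 8.4.3) and to the IDMC (Section 9.1). Appendix 5 requires a DSMB meeting before Dosage B, with unblinded review of individual safety data and stopping rules still to be set. Opening Dosage B at 0/6 is thus not automatic. This stands as mitigation, but none of these steps adds the event to the count that Sections 6.5 and 6.6 use.

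The readings do not carry equal weight. The literal one exempts an event because it fails to resolve, and requiring 7 days for every reaction would be odd for a fatal one. That is fair, but the natural reading alone produces the gap.

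The exception may also be deliberate, since Section 6.7.1 anticipates a temperature rise. That section speaks of a mild rise, however, and a wish to excuse transient fever does not explain why the shorter one counts and the longer one does not.

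Finally, one could assume DLT rates of 33% or 50% and report a 26% or 50% chance that the three skipped patients would have brought a halt. Nothing in the documents supports such rates.

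**Conclusion.** The definition is wrong as written and should be corrected. On the natural reading, drug-related fever above 40.0 C lasting more than 24 hours and resolving within 7 days is not a DLT, while a fever of the same height lasting up to 24 hours is. The conclusion rests on the legible Grade 3 text in Appendix 4 and on reading the list as exceptions.

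The consequence is one patient's classification in a likely rare event. That is enough to change the action at 1 against 0 or 3 against 2, but it has little effect on the estimated DLT rate.

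Three stronger inferences are not supported:

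- That every reading ranks a milder fever above a worse one. Only the first three rows of the readings table do so.
- That the item is a slip for 24 hours or less. The documents do not say what was intended.
- That such fevers would go unmonitored. SAE reporting and DSMB review still apply.

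**What to change.** Make the same change in Section 6.6 and in both Synopsis entries (Study Overview and Safety Evaluation):

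- Delete the fever item, so that any drug-related fever of Grade 3 or higher is a DLT.
- Reword the clause to: *except laboratory results and Grade 3 fatigue, pain or headache, which count as a DLT only if still unresolved after 7 consecutive days despite medical treatment.*

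The 20-hour, 5-day and 8-day fevers then all count, and the 7-day allowance for the other items is kept as on the natural reading. A sentence making any Grade 4 or 5 non-laboratory drug reaction a DLT is optional.

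Do not simply change the item to 24 hours or less. A fever that short can never meet a 7-day condition, so Grade 3 fever, which counts now on the natural reading, would stop counting.

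The cost is one deleted line and one reworded clause in three places, plus the matching CRF definition. Slightly more events may count as DLTs. On the natural reading these are only fevers above 40.0 C lasting more than 24 hours and under 7 days. There would be more if the sponsor has been applying a stricter reading of the 7-day clause.
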